3.2 Executive Committee

THAPCA will be governed by an Executive Committee (Figure 1). The Executive Committee will consist of the chairpersons of each of the two networks, a lead investigator from each of the two networks, a representative investigator from the current Canadian pilot study, two investigators from the Data Coordinating Center (DCC), and Federal representatives from the funding agency of this trial (NHLBI) and the funding agencies of the two networks. Consultants include a principal investigator from the NICHD

neonatal hypothermia RCT, a pediatric neurologist, and a pediatric cardiologist. Additional experts are anticipated to be consulted by the Executive Committee and may be added to the Executive Committee if deemed necessary by the members already listed.

The Executive Committee will be empowered to make all necessary decisions on behalf of the THAPCA Trials. It is anticipated that the Executive Committee will meet on a monthly basis, by teleconference or in person.

3.3 Steering Committee

The Steering Committee will consist of all investigators participating in THAPCA, as well as all members of the Executive Committee. Due to its large size, the Steering Committee is advisory to the Executive Committee. It is anticipated that the entire Steering Committee will meet at least twice annually, once in person and additional meetings by teleconference.

3.4 Study Coordinators

The research coordinators for this study will ideally meet twice per year to facilitate initial and on-going study training. One of these meetings may coincide with the Steering Committee, but logistical issues may make this impossible. The DCC staff will prepare all training materials, in conjunction with the lead THAPCA investigators, and will staff the training meetings.

The DCC staff will meet by teleconference with the research coordinators bi-monthly or as needed to facilitate the execution of the project. After the trial has been underway for at least one year, the frequency of these meetings may be decreased at the discretion of the DCC staff.

3.5 Data Safety Monitoring Board

The Data Safety Monitoring Board (DSMB) will be appointed by the National Heart, Lung, and Blood Institute (NHLBI). Its logistics will be handled by DCC. More details are provided in [Section 11.1 on page 72](#).

4 Study Hypotheses and Endpoints

4.1 Study Hypotheses

The hypotheses of the THAPCA Trials are that (1) therapeutic hypothermia will improve survival and neurobehavioral outcome following out-of-hospital

cardiac arrest in children (THAPCA-OH Trial); and (2) therapeutic hypothermia will improve survival and neurobehavioral outcome following in-hospital cardiac arrest in children (THAPCA-IH Trial). These hypotheses will be tested independently.

4.2 Primary Endpoint

The primary endpoint of each THAPCA trial is survival with good neurobehavioral outcome at 12 months post arrest. The Vineland Adaptive Behavior Scales (VABS-II) will be used to provide a standardized, quantifiable measure of neurobehavioral function in survivors. Poor neurobehavioral functioning is defined as a standardized VABS-II score less than 70 at 12 months. Children with a pre-cardiac arrest baseline VABS-II standardized score less than 70 will be included in the trials but will be excluded from analysis of the primary outcome. Pre-cardiac arrest baseline VABS-II information will be completed retrospectively by the caregiver (as soon as possible after enrollment to decrease retrospective bias), and the 12 month VABS-II assessment will be conducted centrally by telephone interview by the Kennedy Krieger Institute (Johns Hopkins School of Medicine, Baltimore, MD).

4.3 Secondary Endpoints

Secondary endpoints of each THAPCA trial are:

1. Survival at 12 months post cardiac arrest;
2. Change in neurobehavioral function from pre-cardiac arrest baseline to 12 month measurement (VABS II);

For survivors only,

3. Neuropsychological scores at 12 month evaluation;
4. Neurological abnormality scores at 12 month evaluation.

4.4 Safety Endpoints

Safety endpoints of this study are:

1. All-cause 28 day mortality;

2. Incidence of culture proven infection (blood, urine, respiratory, or other) within 7 days of cardiac arrest;
3. Incidence of arrhythmias within 7 days of cardiac arrest;
4. Blood products required within 7 days of cardiac arrest. Blood products are defined specifically here to include red blood cells, platelets, fresh frozen plasma, and cryoprecipitate.

5 Patient Eligibility and Accrual

The study population is the pediatric population greater than 48 hours and less than 18 years of age who experience cardiac arrest for two minutes or longer with return of spontaneous circulation (ROSC/ROC).

5.1 Inclusion Criteria

Patients will be eligible for enrollment if they meet *all* of the following inclusion criteria:

- patient suffered cardiac arrest requiring chest compressions for at least 2 minutes (120 seconds) with ROSC/ROC for at least 20 minutes; AND
- age greater than 48 hours (with a corrected gestational age of at least 38 weeks) and less than 18 years; AND
- patient requires continuous mechanical ventilation; AND
- the cardiac arrest was unplanned (i.e., not part of cardiac surgical procedure)

5.2 Exclusion Criteria

Patients will be ineligible for enrollment if *any* of the following exclusion criteria are met:

- the parent or legal guardian does not speak English or Spanish (the only two languages in which VABS II is standardized)
- randomization is impossible within six hours of ROSC; OR

- patient is on extracorporeal membrane oxygenation (ECMO) when arrest occurs; OR
- continuous infusion of epinephrine or norepinephrine at very high doses ($\geq 2 \mu\text{g}/\text{kg}/\text{minute}$) received immediately prior to randomization; OR
- Glasgow Coma Scale motor response of five (localizing pain or for infants less than two years, withdraws to touch) or six (obeys commands, or for infants, normal spontaneous movement) prior to randomization; OR
- history of a prior cardiac arrest with chest compressions for at least two minutes during the current hospitalization but outside the 6 hour window for randomization; OR
- pre-existing terminal illness with life expectancy < 12 months; OR
- lack of commitment to aggressive intensive care therapies including do not resuscitate orders and other limitations to care; OR
- cardiac arrest was associated with severe brain, thoracic, or abdominal trauma; OR
- active and refractory severe bleeding prior to randomization; OR
- near drowning in ice water with patient core temperature $\leq 32^\circ\text{C}$ on presentation; OR
- patient is pregnant; OR
- patient participation in a concurrent interventional trial whose protocol, in the judgment of the THAPCA investigators, prevents effective application of one or both THAPCA therapeutic treatment arms, or otherwise significantly interferes with carrying out the THAPCA protocol; OR
- patient is newborn with acute birth asphyxia; OR
- patient cared for in a neonatal intensive care unit (NICU) after arrest (ie, would not be admitted to PICU); OR
- patient has sickle cell anemia; OR
- patient known to have pre-existing cryoglobulinemia; OR

- central nervous system tumor with ongoing chemotherapy or radiation therapy; OR
- chronic hypothermia secondary to hypovolemic, pituitary, or related condition for which body temperature is consistently below 37 °C ; OR
- progressive degenerative encephalopathy; OR
- any condition in which direct skin surface cooling would be contraindicated, such as large burns, decubitus ulcers, cellulitis, or other conditions with disrupted skin integrity (NOTE: patients with open chest CPR should be included but placement of cooling mattresses will be modified as needed); OR
- previous enrollment in the THAPCA Trials.

5.3 Decision to Enroll Subject

Participation in THAPCA should be offered to all patients who meet inclusion and exclusion criteria, unless:

- the attending physician does not wish the patient to be offered the opportunity to participate in the study; OR
- the site investigator and/or study coordinator are unable to recruit an additional patient into the study at the time that a new eligible patient is identified.

Parents or legal guardians who are not approached because the attending physician does not wish the patient to be offered participation in the study will be tracked by the DCC in order to assure that enrollment bias does not occur. The attending physician will be asked for the specific reasons for not offering participation for the patient.

5.4 Subject Withdrawal

All patients withdrawn early from the study must have a reason for withdrawal recorded on the appropriate data collection form, and the circumstances leading to withdrawal must be described. All adverse events leading to withdrawal of study interventions must be fully documented and followed up as appropriate. This is particularly important when adverse events are

ongoing at the time of withdrawal, but the reason for withdrawal is not related to the adverse event.

If the study intervention is discontinued by the clinical care team because of adverse events, this does not constitute subject withdrawal from the study. All cases randomized in this study will be analyzed as an intention-to-treat.

If a subject's parents withdraw permission for the subject to continue in the study, all study interventions will be discontinued. The medical course of the subject will continue to be reviewed for adverse events until Day 14. If the subject experienced an Adverse Event from the time of randomization through Day 14 that has not resolved by Day 14, the Adverse Event will be followed until resolution or discharge, whichever is earlier. If the Adverse Event has not resolved by hospital discharge, please see section 11.2.6 of the protocol for further instructions.

5.5 Inclusion of Women and Minorities

The gender, ethnic, and racial composition of patients enrolled in the THAPCA Trials will be a function of the underlying referral population at each participating clinical center. Subjects from our retrospective chart review of cardiac arrest patients (Section 2.4 on page 20) were 47% white, 27% black, and 6% Hispanic. During this study, the DCC will monitor patient accrual by race, ethnicity, and gender.

5.6 Anticipated Recruitment and Study Duration

The planned duration of the study is six years; five years will be used for patient recruitment and one additional year for patient follow up. It is anticipated that participating sites will recruit between 5 and 20 patients annually. Based on HD044955 cohort pilot data and the size and number of sites participating in the current study, we anticipate enrolling between 150 to 250 patients per year for a total enrollment of 750 to 950 patients (300 to 350 out-of-hospital arrests and 450 to 600 in-hospital arrests).

5.7 Long Term Follow-up

Children who were enrolled in the THAPCA Trials represent a very valuable group to study for long term cognitive, developmental and medical sequelae. The subjects legal representative will be approached for consent to be contacted for future studies when deemed appropriate by the clinical centers IRB (i.e. at time of THAPCA consent, between 3 and 12 month visits or after the 12 month visit as appropriate).

6 Study Design & Methods

The THAPCA Trials are two prospective randomized controlled trials of therapeutic hypothermia after cardiac arrest in children. Each THAPCA Trial will be analyzed as an intention to treat study. The THAPCA Trials include one for out-of-hospital cardiac arrests (THAPCA-OH Trial), and one for in-hospital cardiac arrests (THAPCA-IH Trial) (see Figure 2). These trials will be analyzed separately, because etiologies and patient outcomes of these groups are substantially different (see Section 2.3.2 on page 18).

[figure not shown]

Figure 2: THAPCA Trials Diagram

The clinical care team (composed of physicians, nurses, and others) involved with direct patient care and the patient’s family will not be blinded to the treatment group, because temperature is a routine vital sign required for patient care. However, individuals who conduct assessment of neurobehavioral outcome status at three and 12 months following CA will be blinded to the treatment group assignment.

6.1 Screening, Enrollment, and Randomization

Clinical investigators in each site will be pediatric critical care or emergency medicine specialists; in many sites, there will be an assigned investigator in the intensive care unit and in the emergency department. The THAPCA-OH (out-of-hospital) Trial will be enhanced by close cooperation between specialists in the emergency medicine and critical care.

For cardiac arrest cases occurring in the in-hospital (IH) setting, screening will be straightforward. The assigned study physician will be notified by the clinical team as soon as possible after the ROSC/ROC occurs. In the out-of-hospital (OH) setting, the emergency medicine (EM) staff will similarly notify the assigned study physician who performs screening of cases of any arrests occurring in or coming to the emergency department. In the event of a case at another facility, the PICU or EM clinical team arranging the transport will notify the study physician for screening.

The assigned study physician will screen/review each patient for potential eligibility. A screening log will be completed for all CA patients, whether eligible or not eligible. If a patient meets inclusion/exclusion criteria for study participation, the subject's parent(s)/guardian(s) will be approached for written informed permission for the child to participate in the appropriate THAPCA trial (see Section 10.2 on page 66). Following written permission, patients will be randomized to hypothermia treatment or normothermia control therapy. Patients must be randomized within six hours of ROSC/ROC.

Note: Pregnancy is a contraindication for participation in this study. All female patients of child-bearing potential must have a negative urine or blood pregnancy test prior to enrollment.

Randomization for each trial will be stratified by clinical center and patient age group (less than 2 years, 2 to 11 years, 12 years or older). The DCC will prepare randomization schedules using randomized blocks of varying length for each of these study strata. Patients within each stratum will be randomized in a 1:1 ratio to hypothermia or normothermia. Patient randomization will be accomplished using either an Internet connection to the DCC, or an interactive telephone service.

We expect participating centers to maintain equipoise with respect to the use of TH after CA in children. While we cannot prohibit the use of TH outside of the THAPCA Trials, we will track how many eligible patients were not approached for enrollment in the study by center. In addition, we will obtain information about the use of off study hypothermia as well as baseline cardiac status of all children meeting inclusion criteria but not enrolled in the study. If there are clinical centers in which the therapy is frequently offered outside of THAPCA, these centers will be dropped from the study due to concerns of enrollment bias.

6.2 Overview of Interventions

Patients will be randomly assigned to receive either therapeutic hypothermia or normothermia (control) therapy in a 1:1 ratio. See Figure 3 on the next page for an overview of the intervention timeline. Therapeutic hypothermia is defined as surface cooling to 32-34 degrees Celsius ($^{\circ}\text{C}$), for a total duration of 48 hours. This will be followed by slow rewarming to normal temperature (36.0-37.5 $^{\circ}\text{C}$ range) over approximately 16 hours. The control group will have patient temperature maintained within the defined normothermic range (36-37.5 $^{\circ}\text{C}$). Normothermia will be maintained in the control arm during the periods corresponding to cooling, hypothermia, and rewarming of the hypothermia arm. Both study groups will then have temperature maintained in the normal range (36-37.5 $^{\circ}\text{C}$) until 120 hours post cardiac arrest ROSC/ROC. Thereafter, temperature will be maintained as is practiced routinely in the clinical center's PICU. See Section 7 on page 45 for a detailed outline of the interventions, patient monitoring, and concomitant therapies.

6.3 Laboratory Testing

Laboratory testing will be conducted throughout the intervention period (0 to 120 hours). The schedule of assessments is similar for the the two assigned treatment groups.

Electrolytes (sodium, potassium, bicarbonate, blood urea nitrogen (BUN), creatinine, glucose, chloride) will be monitored at the following timepoints:

For the Hypothermia Group:

- During Active Cooling and Re-warming: electrolytes will be completed at least every 6 hours. If electrolytes are drawn more frequently than once every 6 hours, all values will be recorded
- During Hypothermia and Normothermia: electrolytes will be completed at least every 12 hours. If electrolytes are drawn more frequently than once every 12 hours, those values drawn closest to 8 am and 8 pm will be recorded.

For the Normothermia Group:

- If active cooling/warming is required to get the subject to normothermic temperature; electrolytes will be completed at least every 6 hours. If electrolytes are drawn more frequently than every 6 hours, all values will be recorded.

[figure not shown]

Figure 3: Timeline of Study Interventions

- During Normothermia: electrolytes will be completed at least every 12 hours. If electrolytes are drawn more frequently than once every 12 hours, those values drawn closest to 8 am and 8 pm will be recorded.

Other blood monitoring during the intervention period will include daily complete blood count (CBC), liver function tests (LFTs), specifically alanine aminotransferase (ALT), aspartate aminotransferase (AST), bilirubin (BILI), prothrombin time (PT) and International Normalized Ratio (INR), partial thromboplastin time (PTT), amylase, lipase, magnesium, calcium, and phosphorous. All values obtained during the intervention period (through 120 hours) will be recorded. These values should be obtained at a minimum of once per day.

Arterial blood gas (ABG) and lactate measurements will be monitored daily for the first 72 hours. Subjects are anticipated to have frequent ABG measurements. If there are multiple measurements during any study day, the measurement closest to 8:00 A.M. will be recorded.

Blood cultures will be obtained at the time of randomization and on days 1, 2, and 3. Days are defined as 24 hour periods from 12:00 a.m. to 11:59 p.m. Day 1 is the first full 24 hour period after randomization. Urine cultures will be obtained at the time of randomization and on days 2 and 4. The final results of all cultures sent within 7 days of enrollment will be obtained and recorded in the database.

Chest x-rays will be done daily during the intervention period in order to confirm temperature probe position. If multiple radiographic examinations are obtained during any study day, the examination closest to 8:00 A.M. will be recorded.

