11.2.3 Data Collection Procedures for Adverse Events

After patient randomization, all adverse events (including serious adverse events), whether anticipated or unanticipated, will be recorded according to the date of first occurrence, severity, and their duration, as well as any treatment prescribed. Any medical condition present at the time of randomization, recorded in the patient's baseline history at study entry, which remains unchanged or improves, will not be recorded as an adverse event at subsequent evaluations. However, worsening of a medical condition that was present at the time of randomization will be considered a new adverse event and reported.

Abnormal laboratory values that are clinically significant will be recorded as adverse events and the clinical site investigator will assess the severity and relationship to the study. Laboratory values that are abnormal at the time of randomization and that do not worsen will not be recorded as adverse events.

Adverse events will be coded using the MedDRA coding vocabulary. Coding will be done centrally at the DCC because this requires specific training.

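### Protocol 6.3 makes electrolyte and glucose ascertainment depend on arm during the cooled arm's cooling and rewarming hours, so extremes recorded there are not comparable between arms at face value

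*Protocol*

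**What the plan says.** Protocol section 6.3 defines the electrolyte panel as sodium, potassium, bicarbonate, BUN, creatinine, glucose and chloride, and sets the rules by arm and phase.

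- **Hypothermia arm, changing temperature:** "During Active Cooling and Re-warming: electrolytes will be completed at least every 6 hours", and "If electrolytes are drawn more frequently than once every 6 hours, all values will be recorded".
- **Hypothermia arm, 48 h of maintenance and later normothermia:** "During Hypothermia and Normothermia: electrolytes will be completed at least every 12 hours"; extra draws fall under the 8 am/8 pm rule, "If electrolytes are drawn more frequently than once every 12 hours, those values drawn closest to 8 am and 8 pm will be recorded".
- **Normothermia arm, in range:** "During Normothermia: electrolytes will be completed at least every 12 hours", with the same 8 am/8 pm rule.
- **Normothermia arm, not yet in range:** "If active cooling/warming is required to get the subject to normothermic temperature; electrolytes will be completed at least every 6 hours", with all values recorded.

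The section introduces this with "The schedule of assessments is similar for the the two assigned treatment groups". For the daily blood tests (blood count, liver tests, coagulation, magnesium, calcium, phosphorus and others), it records every value through 120 hours in both arms.

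**The concern.** Over the hours in which the cooled arm is cooled or rewarmed, a control already in range has half the minimum sampling rate. Any control draws beyond that minimum are cut back to two clock-time values a day, while the cooled arm keeps everything. The more values a child has on file, the more likely one of them is extreme, even if physiology is the same in both arms.

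The difference falls where a signal is expected. Sections 7.7 and 10.4.2 describe potassium falling on cooling and rising on rewarming, and 7.7 asks sites to avoid extremes of potassium and glucose. Section 10.4.1 cites potassium and glucose differences from earlier cooling trials, so readers will look for this comparison. A table of hypokalaemia, hyperkalaemia or glucose extremes by arm would mix a real effect with unequal ascertainment. A later analysis plan cannot restore control values that were never entered.

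**Working it through.** The plan states no figure to reproduce. The check counts draws and then asks what unequal counts do when the arms do not differ.

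**Inputs from the protocol.** Cooling takes 1 to 4 h and maintenance 48 h. Rewarming takes about 16 h, with its end placed at about 72 h after the start (section 7.1). The intervention period is 120 h, and the draw minimums are 6-hourly and 12-hourly (section 6.3).

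**Hours in which the rules differ** (control already in range):
- shortest: 1 + 16 = 17 h;
- with 4 h of cooling: 4 + 16 = 20 h;
- if rewarming ends at 72 h: 72 − 48 = 24 h.

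That is 14% to 20% of 120 h. In the other 96 to 103 h the rules are the same.

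**Minimum draws** (hours divided by interval):
- within those hours: 17/6 = 2.8 v 17/12 = 1.4, up to 24/6 = 4.0 v 24/12 = 2.0, a ratio of 2;
- over 120 h: 17/6 + 103/12 = 11.4, up to 24/6 + 96/12 = 12.0, v 120/12 = 10.0, a ratio of 1.14 to 1.20;
- a control needing 1 to 4 h of active warming or cooling: 1/6 + 119/12 = 10.1, up to 4/6 + 116/12 = 10.3. The gap therefore comes mainly from rewarming.

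**Chance of at least one extreme, independent values:** 1 − (1 − p)^n, with the same assumed per-draw risk p in both arms. For 20 differing hours, n = 3.33 v 1.67 in those hours and 11.67 v 10 over 120 h.

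| p (assumed) | In the 20 h | Ratio | Over 120 h | Ratio |
|---|---|---|---|---|
| 2% | 6.5% v 3.3% | 1.97 | 21.0% v 18.3% | 1.15 |
| 5% | 15.7% v 8.2% | 1.92 | 45.0% v 40.1% | 1.12 |
| 10% | 29.6% v 16.1% | 1.84 | 70.7% v 65.1% | 1.09 |

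**Effect of correlation within a child.** Suppose both arms are drawn 4-hourly for 20 h: the cooled arm records 20/4 = 5 values and the control keeps 2. At p = 10%:
- independent values: 41.0% v 19.0%, ratio 2.16;
- latent correlation 0.5: 29.1% v 16.6%, ratio 1.75;
- latent correlation 0.8: 20.9% v 14.3%, ratio 1.46.

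**Simulation over 120 h.** The same autocorrelated process runs in both arms, an extreme is a value beyond 2 SD, and the denser rule applies for 4 h of cooling and 16 h of rewarming. The correlation time is assumed.

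| Correlation time | Minimum draws | Ratio | Both arms drawn 4-hourly | Ratio |
|---|---|---|---|---|
| 6 h | 44.4% v 39.9% | 1.11 | 48.0% v 39.9% | 1.20 |
| 12 h | 41.2% v 37.7% | 1.09 | 43.7% v 37.7% | 1.16 |
| 24 h | 35.5% v 33.4% | 1.06 | 37.1% v 33.4% | 1.11 |

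The second comparison is larger because only the cooled arm keeps the extra values. With 2-hourly draws in both arms the ratio would be 1.17 to 1.34. For rewarming alone, this simulation gave 2.12 to 2.62 at minimum draws. Its fixed clock grid put 3 cooled-arm values against 1 control value in that window, so I do not use those figures as an estimate.

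**Adverse events.** Section 11.2.3 says "Abnormal laboratory values that are clinically significant will be recorded as adverse events", and 11.2.5 has all adverse events through Day 14 entered. Neither section restricts this to values kept under the 8 am/8 pm rule.

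**The case against.** The other side has a good deal to say, and much of it stands.

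- **No planned test uses these values.** The safety endpoints (sections 4.4 and 9.4) are 28-day mortality, culture-proven infection, arrhythmias and blood products. A reader might infer that the formal safety comparisons are biased; they are not.
- **The 8 am/8 pm sentence is common to both arms.** It governs all 48 h of maintenance hypothermia, and the denser rule follows active temperature change in either arm. A reader might infer that recording differs throughout, or that 6.3 contradicts itself by calling the schedules similar. Neither follows: similar is not identical, and the rules match for most of the period.
- **Adverse event capture is separate.** A reader might infer that the recording rule over-detects laboratory adverse events with hypothermia. It cannot, because a clinically significant off-clock value is still reportable. Only draw frequency can act, and since the frequencies are minimums, that effect shrinks where units draw often in both arms.
- **Denser sampling has a stated safety reason** in 10.4.2. This explains the extra draws in cooled children, but not why control values already drawn go unrecorded.
- **An analyst could thin cooled-arm values to 8 am and 8 pm.** That gives a fair comparison of typical levels, but it does not recover control peaks or troughs that were never entered.

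It is also tempting to say that the discarded draws are mostly repeats of abnormal results. The protocol gives no information on that.

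**Conclusion.** The point holds in a limited form. Section 6.3 makes ascertainment of potassium, glucose and the other electrolytes depend on arm for about 17 to 24 of 120 h, mainly rewarming, for controls already in range. With no true difference, recorded extremes in the cooled arm would be inflated by up to about 1.8 to 2.0 times within those hours at minimum draws, assuming 2% to 10% per-draw risk and independent values, and by less if values are correlated. Over the whole 120 h the simulated inflation is roughly 1.06 to 1.20, for draws between the minimum schedule and 4-hourly. The near-doubling must not be read as applying to the full intervention period.

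What is exposed is descriptive laboratory safety data and, through draw frequency alone, laboratory adverse event counts, which the DSMB reviews (11.2.5). The per-draw risks, correlation times and actual draw rates are assumptions; the protocol gives none of them. This is a cheap improvement worth making, not a threat to the trial's main conclusions.

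**What to change.** Leave clinical monitoring as it is and change only what is recorded and how it is compared.

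1. In 6.3, replace the 8 am/8 pm rule with one rule for both arms: record every electrolyte and glucose value already drawn, with its draw time, through 120 h. The section already records all values for the daily blood tests.
2. Base between-arm comparisons on one value per child per matched time window, counted from the start of the intervention in both arms. A 12 h window fits the control arm's minimum frequency.
3. Report per-child peaks and troughs only beside the number of draws in each arm.

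The cost is protocol and case report form wording plus more data entry from charts; no extra blood is taken. Recording alone does not equalise how often children are sampled. Per-child extremes and laboratory adverse events will still rest on unequal draw frequency in these hours, and reports should say so. With matched windows, the number of values compared is equal, and with no true difference the expected ratio is 1.
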